#### Overnight Stay

- Participants will remain overnight in an appropriately furnished room at or near the study site until after the Integrative Session the morning after each Experimental Session. If in line with country specific regulations and site standard operation procedures, with prior approval of the therapy team, a companion may accompany the participant during the overnight stay.
- An attendant will check in periodically on the participant during the overnight stay, even if a companion is present. The attendant will monitor participant condition and will help participants relax during the overnight stay. The attendant will be an individual with previous training in managing psychological distress and will be supportive but not intrusive. If there is an emergency or the participant needs additional support, the attendant can contact the therapy team.
- The participant and a companion (if applicable) will receive information that will allow them to contact the therapy team during the overnight stay in the case of an emergency or to request for additional support.
- Participants will be encouraged to use much of the time during their overnight stay for rest and as a period of reflection and integration in a quiet atmosphere.
- The participant will be driven home after the integration session by either a driver arranged by the participant, by site personnel or taxi.

## 7.3.2 Telephone Contact After Experimental Sessions

The goal of the telephone contact is to assess health changes, ensure participant safety, and offer support. The therapy team will follow-up with the participant by telephone on the second and seventh day after each Experimental Session, with two additional telephone contacts in between. Each call will last on average five to 15 minutes but could be longer to address participant concerns and to adequately assess wellbeing. Additional telephone contact can be initiated at the request of the therapy team or participant.

At each telephone contact, the therapy team will:

- Inquire about any possible changes in health, assess the participant's mental health and
  the status of any previously recorded AEs, and record AEs as described in Section 10.0
  Safety
- Inquire about concomitant medication use and compliance
- Offer support in accordance with the Treatment Manual
- On the second and seventh contact day after an Experimental Session the therapy team will administer the Since Last Visit C-SSRS.

#### 7.3.3 Integrative Sessions

After each Experimental Session, three Integrative Sessions will take place. Each session will consist of 90 minutes of psychotherapy.

#### Treatment 1

- Integrative Session 1.1 (Visit 6): morning after Experimental Session 1 (Visit 5)
- Integrative Session 1.2 (Visit 7): 3 to 14 days after Experimental Session 1 (Visit 5) and at least 2 days after Integrative Session 1.1 (Visit 6)
- Integrative Session 1.3 (Visit 9): within 3 to 5 weeks after Experimental Session 1 (Visit 5) and 1 to 7 days in advance of Experimental Session 2 (Visit 10). At least two days after Integrative Session 1.2 (Visit 7). This visit serves two purposes: to continue integration and to prepare for the next Experimental Session. The participant will complete the LEC-5 and PCL-5 self-report measures.

#### Treatment 2

- Integrative Session 2.1 (Visit 11): morning after Experimental Session 2 (Visit 10)
- Integrative Session 2.2 (Visit 12): approximately 2 weeks after Experimental Session 2 (Visit 10)
- Integrative Session 2.3 (Visit 13): within 3 to 5 weeks of Experimental Session 2 (Visit 10). This visit serves to continue integration. The participant will complete the LEC-5 and PCL-5 self-report measures. For PABP, a final urine pregnancy test will be conducted at this visit, Visit 14 or Visit 15 (representing the end of the relevant systemic exposure, 5 half-lives after the last IMP dose, and at least 2 weeks after the last MDMA experimental session).

During Integrative Sessions, the therapy team will:

- Record the session.
- Inquire about any possible changes in health. Assess the participant's mental health and the status of any previously recorded AEs. Record AEs as described in Section 10.0 Safety.
- Inquire about concomitant medication use and adherence.
- Administer Since Last Visit C-SSRS to determine suicidal risk.
- Discuss and review events that occurred with the participant during the Experimental Session, including thoughts, feelings, and memories. If necessary, the therapy team will help the participant to reduce any residual psychological distress they are experiencing. The therapy teams will also encourage the transfer of states of acceptance, feelings of intimacy, closeness, and reduced fear experienced in Experimental Sessions to emotionally threatening everyday situations. The therapy teams will be supportive, validate the experience, and facilitate understanding and emotional clearing.
- Be accessible for additional support via telephone or tele-assessment if needed.
- At each third Integrative Session, direct the participants to complete the LEC-5.
- At each third Integrative Session, direct the participants to complete the PCL-5.

## 7.3.4 Independent Rater Assessments

Participants will have one CAPS-5 assessment during the first treatment period of the study (Visits 8). An IR from the IR Pool will conduct the assessments via tele-assessment. These assessments may be recorded to establish inter-rater reliability. The results may be shared with site staff, but the IR Coordinator will enter the data. The IR will also administer the DSP-I and SDS at these time-points:

- Baseline CAPS-5 T1 (Visit 3): At least 7 days after Preparatory Session 2 (Visit 2) and confirmation of end of tapering and stabilization off medications and eligibility is confirmed.
- CAPS-5 T2 (Visit 8): 3 weeks (-3/+9 days) after Experimental Session 1 (Visit 5) or 18 to 30 days after Experimental Session 1 (Visit 5), between Integrative Session 1.2 (Visit 7) and Integrative Session 1.3 (Visit 9)
- CAPS-5 T3 (Visit 14): 8 weeks (+/-2 weeks) after Experimental Session 2 (Visit 10), after last Integrative Session 2.3 (Visit 13)

#### 7.4 Follow-up Period and Study Termination

## 7.4.1 Follow-up Period

After the last Integrative Session 2.3 (Visit 13), participants will enter follow-up for approximately 4 weeks (+/- 2 weeks) with no protocol required visits until the final CAPS-5 assessment (Visit 14) followed by a Study Termination (Visit 15). Participants will have access to therapy teams for support if needed, and additional visits via telephone, tele-assessment, or in person can be scheduled if requested. Participants will continue to comply with protocol requirements for concomitant medications until after Study Termination.

## 7.4.2 Final Independent Rater Assessment

Participants will have a final CAPS-5 assessment at the completion of the follow-up period (Visit 14). An IR from the IR Pool will conduct the assessments via tele-assessment. These assessments may be recorded to establish inter-rater reliability. The IR Coordinator will enter the data in stand-alone database. The results may be shared with site staff during supervision by the therapy training team. Although there are allowable windows for all visits throughout the protocol, the Primary Outcome CAPS-5 T3 assessment must be completed 13 weeks (+/- 3 weeks) after the Baseline CAPS-5 assessment and within 8 weeks (+/-2 weeks) of Experimental Session 2 (Visit 10). Participants who have withdrawn from treatment will also complete a final CAPS-5 assessment immediately upon withdrawal. The IR will also administer the DSP-I and SDS.

#### 7.4.3 Study Termination

Study Termination (Visit 15) will take place 2 (-1/+7) days after the final CAPS-5 assessment (Visit 14). Participants who have withdrawn from treatment but have continued for follow-up will also complete this assessment immediately upon withdrawal.

The site team will:

- Inquire about any possible changes in health. Assess the participant's mental health and the status of any previously recorded AEs. Record AEs as described in Section 10.0 Safety.
- Inquire about concomitant medication use and adherence.
- Administer Since Last Visit C-SSRS.
- Conduct symptom-directed physical examination if clinically indicated.
- Conduct pregnancy test (at Visit 13, 14 or 15, or earlier if early withdrawal).
- Measure weight (used to calculate BMI).
- Measure blood pressure.
- Provide and discuss a study exit plan.
- Actively support participant in completion of Study Termination self-reported measures:
  - o LEC-5
  - o PCL-5, ensure assessment is in relation to index trauma
  - o BDI-II
  - o CPGS
  - o EO-5D-5L
  - o SCS
  - o AUDIT
  - o DUDIT
  - o SRNU
  - o EAT-26

Completion of the measures do not need to be recorded.

After all Study Termination measures and assessments are completed, the participant is considered terminated from the study. The participant can resume normal everyday life. The study team will provide an Exit Plan, which may include a referral for additional medical or therapeutic care, as described in Section 7.4.4 Exit Plan. Eligible participants will be asked whether they are interested in participating in the LTFU extension study.

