## 4.3.4 Early Termination from the Study

Participants who are removed from the study after they are enrolled and receive IP but do not complete the study may fall into one of these categories: Post-Dosing Early Termination or Dropout. If the participant has received IP in at least one Experimental Session and completed one CAPS-5 assessment beyond Baseline, they will be considered evaluable. All participants who receive IP in at least one Experimental Session will be included in all safety analyses.

Participants can withdraw from treatment or withdraw consent at any time for any reason without judgment. The site team can withdraw a participant if, in their clinical judgment, it is in the best interest of the participant or if the participant cannot comply with elements of the protocol that are critical for safety or for the scientific integrity of the study. If the site team makes the decision to terminate the participant from treatment or the study, they will explain the reason for withdrawal and document in the participant's source records and eCRF. If a participant develops any Exclusion Criteria that, in the opinion of the Medical Monitor or Site, affects the safety of the participant, including psychiatric diagnosis, pregnancy, or requiring use of prohibited medications, the participant will discontinue treatment in Experimental Sessions but remain in the study for the associated Integrative Sessions. Any time a participant terminates from the study early, the site team will attempt to obtain information about AE outcomes if appropriate, as determined by the site physician and Medical Monitor. The site team will provide the participant with an Exit Plan as described in Section 7.4.4 Exit Plan.

- Post-Dosing Early Termination: Participants who discontinue study treatment but continue to participate in study evaluations and outcome assessments. Data collection by Irs will continue on the same schedule as planned through Study Termination visit procedures.

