#### **8.4 Bias Minimization**

Before a participant is deemed eligible and enrolled into the study, participant's medical history and screening assessments will be reviewed by the Principal Investigator and therapy team. If needed, Medical Monitor will be consulted.

Two different processes exist to ensure bias minimization: the primary and secondary outcome assessments performed by the IR team will be recorded and then reviewed by a senior (local) IR, and all psychotherapy study visits (including the experimental sessions) will be reviewed by adherence raters to ensure adherence to the Treatment Manual, and consistency among therapy pairs and sites. The paragraphs below describe these processed in more detail.

To minimize bias in measuring effect, the sponsor will use an observer-blind, centralized, reliable IR pool to administer the Primary Outcome measure via live video interviews. The IR Pool will have no knowledge of participant's study data or AEs and will only evaluate participants at Baseline and at the assessments scheduled after each Experimental Session. The IR Pool is blinded to study design, visit number, number of treatments, and any data from the treating therapy team after Baseline. IRs will be assigned to participants based on availability. Data will be entered into a dedicated IR Database by the IR Coordinator who is not part of the study assessments or procedures. Timing of CAPS-5 assessments are provided in Table 2.

To ensure that all participants are treated in a similar manner, the sites will be required to follow the protocol and Treatment Manual delineating minimum length of time per visit type and describing delivery of treatment. All Experimental Sessions are required to be at least 8 hours long. Adherence to the Treatment Manual will be checked by review of video by adherence raters. The sponsor will monitor data in real-time to ensure complete data collection for all participants, including those who discontinue treatment. Sites will be required to make and document a specific number of attempts to obtain follow-up data per protocol. All participants who receive at least one dose of IP and complete at least one follow-up assessment will be included in the final mITT analysis.

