#### 11.3 Prohibited Medications

To be enrolled in the study participants must:

- Refrain from the use of any psychoactive medication not approved by the research team from Baseline through Study Termination (with the exception of gabapentin or certain opiates for pain control).
- Be willing to comply with all medication requirements per protocol. Medications will only be discontinued after enrollment per clinical judgment of the site physician in consultation with the prescribing physician.
- Agree that, for 1 week preceding each Experimental Session to refrain from:
  - o Taking any specified herbal supplement (except with prior approval of the research team).
  - Taking any nonprescription medications (with the exception of non-steroidal anti-inflammatory medications or acetaminophen) unless with prior approval of the research team.
  - o Taking any prescription medications (with the exception of birth control pills, thyroid hormones, or other medications approved by the research team).

The research team should only approve medications that clearly would not be expected to have any interactions with MDMA, including, but not limited to, any drugs with sympathomimetic

activity or activity on the serotonin or other monoamine systems, and any other drugs that would be contraindicated with or have any interaction with monoamine oxidase inhibitors (MAOIs).

The following medications are prohibited as they would present potential confounds for interpretation of the data collected from this study as they have notable serotonergic effects or are under potential or available treatments for PTSD:

Use of Marijuana, St. John's Wort, and other herbs and medicines with notable serotonergic effects are prohibited from Baseline to Study Termination. Any investigational treatments under study for PTSD treatment are prohibited from use concurrent with this study.

Diphenhydramine is excluded from this study unless prior approval is granted by the site physician.

If an SSRI, SNRI, or other antidepressant is used between Experimental Session 1 (Visit 4) and Study Termination (Visit 15), the participant will be withdrawn from treatment and continue in follow-up.

Opiates other than hydrocodone, morphine, and codeine are prohibited from Enrollment Confirmation to Study Termination. Participants taking prohibited opiates will be cross-tapered to an allowable opiate during the Preparatory Period.

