8.2 Missing Data Handling

All possible procedures within Good Clinical Practice (GCP) will be used to minimize Postdosing Early Termination. Based on the US Phase 2 data it is expected that up to 5% of enrolled and randomized participants will terminate early. Post-dosing Early Terminators will be compared to the Completers using baseline demographics and CAPS-5 Total Severity Score at baseline. Participants who are removed from the study after they are enrolled and receive IP but do not complete the study may fall into one of these categories: Post-Dosing Early Termination or Dropout. If the participant has received IP in at least one Experimental Session and completed one CAPS-5 assessment beyond Baseline, they will be considered evaluable. All participants who receive IP in at least one Experimental Session will be included in all safety analyses. Post-Dosing Early Termination are participants who discontinue study treatment but continue to participate in study evaluations and outcome assessments. Data collection by IRs will continue on the same schedule as planned through Study Termination visit procedures. Dropouts are defined as a participant who decides to withdraw consent. They will terminate without further follow-up. If the participant agrees, they will complete a final CAPS-5 assessment and Study Termination visit procedures. These participants are defined as dropouts who withdraw consent due to any reason after receiving at least one dose of IP and no longer participate in the study, i.e. no further contact with investigators or site staff. Data collected on study participants up to the time of withdrawal of consent will remain in the trial database in order to maintain scientific validity. All observed CAPS-5 data up to the point of discontinuation of treatment will be included in the MMRM model of the *de jure* estimand from Post-dosing Early Terminators. Participants will not be replaced. All observed CAPS-5 data from Post-dosing Early Terminators and Dropouts collected prior to and after early termination will be included in the supportive effectiveness analysis of the *de facto* estimand.

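### Protocol 7.4.3, read literally, closes out treatment stoppers at withdrawal, while Protocol 4.3.4 and SAP 8.2 keep them on the rater schedule through V14

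*Protocol*

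**What the plan says.** Protocol 7.4.3 places Study Termination (V15) shortly after the V14 CAPS-5 and adds, for treatment stoppers: "Participants who have withdrawn from treatment but have continued for follow-up will also complete this assessment immediately upon withdrawal". Later in the same section: "After all Study Termination measures and assessments are completed, the participant is considered terminated from the study". Protocol 7.4.2, after setting the V14 window, says: "Participants who have withdrawn from treatment will also complete a final CAPS-5 assessment immediately upon withdrawal".

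Protocol 4.3.4 defines a Post-Dosing Early Termination as someone who stops study treatment but goes on with evaluations and outcome assessments. It says of this group: "Data collection by Irs will continue on the same schedule as planned through Study Termination visit procedures". SAP 8.2 repeats the rule: "Data collection by IRs will continue on the same schedule as planned through Study Termination visit procedures". Three further places point the same way:

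- Protocol 4.3.4, on participants who develop an exclusion criterion that affects their safety: "the participant will discontinue treatment in Experimental Sessions but remain in the study for the associated Integrative Sessions".
- Protocol 8.4: "The sponsor will monitor data in real-time to ensure complete data collection for all participants, including those who discontinue treatment".
- Protocol 11.3, on antidepressant use during the study: "the participant will be withdrawn from treatment and continue in follow-up".

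SAP 8.2 uses CAPS-5 scores from before and after early termination in a supportive analysis of the de facto estimand. SAP 8.7.1 leaves CAPS-5 collected after treatment discontinuation out of the de jure estimand.

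On replacement, Protocol 4.3.4 allows it for dropouts and those lost to follow-up, depending on timing and on the video available for supervision. SAP 8.2 rules it out without qualification.

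**The concern.** The two sets of instructions concern the same people, and one person cannot be closed out when treatment stops and also be rated at V14. A site that follows 7.4.3 to the letter would do the immediate CAPS-5 and the Study Termination visit and then stop. The scheduled V14 score would not be collected from someone who was still willing to give it. V8 would be lost too if it had not yet taken place, and the V15 questionnaires would be taken weeks early.

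The de facto analysis exists to show what happens to people who stop treatment, and these are the scores it would be missing. A score that was never collected cannot be recovered in analysis. SAP 8.2 also has no rule for placing an off-schedule CAPS-5 at a visit.

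**Working it through.** **1. Same group?** Protocol 7.4.3 speaks of people withdrawn from treatment who have continued in follow-up. Protocol 4.3.4, SAP 1.0 and SAP 8.2 define Post-Dosing Early Terminations as people who stop treatment and continue assessments. These are the same people.

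**2. Reproduce the V14 window.** Table 1 gives V5 at 4 to 7 days after V3, V10 at 21 to 35 days after V5, and V14 at 42 to 70 days after V10.

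- Opening: 4 + 21 + 42 = day 67.
- Close: 7 + 35 + 70 = day 112.

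Both match Table 1's day range of 67 to 112 after baseline.

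**3. When would the immediate CAPS-5 fall?** Take a stop after Session 1 and no later than the planned Session 2.

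- Earliest: V5 at day 4.
- Latest: V10 at 7 + 35 = day 42.
- Gap to the opening of the V14 window: 67 − 42 = 25 days to 67 − 4 = 63 days.
- Gap to the 13-week target (13 × 7 = day 91): 91 − 42 = 49 days to 91 − 4 = 87 days.

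So no such assessment can count as an in-window V14.

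**4. Is V8 also at risk?** Table 1 puts V8 at 18 to 30 days after V5, which is day 4 + 18 = 22 to day 7 + 30 = 37 after baseline. Someone who stops before their V8 and is closed out loses both V8 and V14.

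**5. How many people?** SAP 8.2 expects up to 5% to terminate early, and the protocol plans up to 40 participants. The expected count is 0.05 × 40 = 2. With X the number of early terminators, binomial with n = 40 and p = 0.05:

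- P(X ≥ 1) = 1 − 0.95^40 = 87%.
- P(X ≥ 2) = 60%.
- P(X ≥ 3) = 32%.

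For comparison, Protocol 1.2.4 reports dropout of 8/107 = 7.5% in earlier studies, which would give 0.075 × 40 = 3.

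**6. Which analyses depend on these scores?**

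| Analysis | Exposed? | Reason |
|---|---|---|
| Primary de jure (SAP 8.7.1) | No | CAPS-5 after treatment discontinuation is excluded either way |
| Supportive de facto (SAP 8.2) | Yes | Uses CAPS-5 collected after early termination |
| Responder summary at T3 (SAP 8.7.4) | Yes | No on-treatment restriction is stated |
| V4-to-V15 exploratory measures (Protocol Table 4) | Yes | V15 would be taken at withdrawal |

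**The case against.** The strongest reply is that the literal reading makes 7.4.3 contradict itself, because someone who has continued in follow-up cannot be terminated on the day treatment stops. The sentence may therefore mean a later withdrawal from the study. Protocol 10.3.3 ties an immediate final CAPS-5 to leaving the study, and 4.3.4 gives dropouts a final CAPS-5 when they leave. Alternatively, the word also in 7.4.2 and 7.4.3 may mark an extra visit on top of V14 and V15. The section that governs early termination, the SAP, and Protocol 8.4 and 11.3 all keep stoppers in assessment.

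This stands as a possible intention, but the text does not say it. The only withdrawal named in either sentence is from treatment. An extra-visit reading also fits poorly with calling the immediate CAPS-5 final and with counting the participant as terminated once Study Termination is done. The milder reading makes this a drafting conflict with a conditional consequence. It does not tell a site which instruction to follow.

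Four stronger inferences are tempting but not supported:

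- **The primary result is at risk.** SAP 8.7.1 rules this out.
- **Two participants is the most that could be affected.** It is an expected count at the planning rate, and three or more would occur with probability of about 32%. The 5% may also include dropouts, who are not the group at issue.
- **The early CAPS-5 would stand in for V14.** No section says so, and SAP 8.7.1 says missing data are not imputed. The early score remains observed data, and the SAP is merely silent on its visit assignment.
- **Replacement would take the number dosed above 40.** The protocol's recruitment section caps enrolment at 40, while the synopsis study design speaks of up to 40 who complete. The documents do not settle it.

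It is also fair to say that the replacement conflict concerns a different group and has negligible analytic effect. Nobody leaves an analysis set because of it.

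**Conclusion.** The conflict is real and in current text. Its severity is minor. Under a literal reading of 7.4.3, a willing participant who stops between V5 and the planned V10 has the last CAPS-5 25 to 63 days before the V14 window opens and gives no V14 score. About 2 early terminators are expected among 40 at the SAP's rate, and the number who stay in follow-up may be smaller. The exposure is confined to supportive and exploratory results in a single-arm study without a power calculation.

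This rests on three assumptions:

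- The site follows 7.4.3 rather than 4.3.4.
- The V14 window is counted from baseline, as in Table 1. Table 6 counts 13 weeks ± 3 from V5, so it opens 70 days after V5, and a stop at most 35 days after V5 would then be at least 70 − 35 = 35 days early.
- The de facto analysis is read at 13 weeks. SAP 8.2 gives it no time point, and SAP 8.7 gives it no model.

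**What to change.** - **Protocol 7.4.2 and 7.4.3:** reconcile with Protocol 4.3.4 and SAP 8.2. State that, for participants who stay in the study, any assessment at treatment withdrawal is additional to, and does not replace, the remaining scheduled CAPS-5 visits (V8 if still due, and V14) and V15. Which safety checks are done at withdrawal is for the sponsor to reconcile.
- **SAP 8.2:** record a CAPS-5 taken because of withdrawal as unscheduled, at its actual day.
- **Replacement:** state one rule in Protocol 4.3.4 and SAP 8.2, and keep every dosed participant in the disposition and attrition denominator.

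The cost is a few sentences, plus one or two rater tele-assessments per stopper who stays (two if the stop precedes V8), at about 77 minutes each in Table 7. For two stoppers that is 2 × 77 = 154 to 4 × 77 = 308 minutes in total. Protocol 4.3.4 and SAP 8.2 already call for these assessments.
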